### **3. TRIAL DESIGN**

This is a two-arm, open-label, randomized controlled study. Men and women between 50-75 years of age who have never undergone a screening test for colorectal cancer (and who have no known history of Ulcerative Colitis, Crohn's disease, Familial Adenomatous Polyposis, Lynch Syndrome, Personal history of colon cancer) will be randomized to the colorectal cancer risk information arm (CRCRAT arm) or to the no risk information arm (control arm). The study period for subjects will end approximately 12 months post-randomization.

Stanford Primary Care Clinic subjects who meet eligibility criteria will be identified through a pre-existing outreach list. A brief chart review will be conducted to ensure subjects meet particular inclusion/exclusion criteria. A letter will be sent to eligible subjects (along with the HIPAA authorization form), describing the research study and informing subjects that they will be contacted in the near future. Subjects will be provided with the option to "opt-out" of being contacted. Subjects will be contacted a few weeks later to give all subjects adequate time to respond.

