Eligible subjects will be contacted using an approved telephone script to provide verbal consent for participation in the study. If a subject agrees to participate in the study, they will be immediately randomized, using blocked randomization, to either the CRCRAT or control arm. Both groups will then undergo a pre-intervention survey designed to assess attitudes towards colorectal cancer screening. Study interventions will be administered during this same telephone encounter. The control and intervention arms will both be read general information about colorectal cancer. The CRCRAT arm will then be guided through a series of questions from the NCI Colorectal Cancer Risk Assessment Tool in order to calculate their personalized risk of colorectal cancer. This personalized risk score will be recorded and subjects will be provided with the information on their risk scores. Immediately following these interventions, both arms will undergo a post-intervention survey, which again assesses attitudes towards colorectal cancer screening. Over the next 6 and 12 months, subjects' electronic medical records will be reviewed for colorectal cancer screening status. Subjects who were not screened, per their electronic medical record, will be contacted via phone or mail to see if they were screened elsewhere and/or assess their current screening intent. Subjects will be contacted no more than 3 total times for this research study.

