### **3.2 Sample Size justification**

A clinically significant improvement in the screening rate would be greater than or equal to 10-20%.

To calculate the appropriate sample size necessary for this study, we assumed uniform accrual over a 6-month period and minimum follow-up of 12 months for all subjects.

Further assuming that the current standard has a screening rate of 50% by 6 months (or event rate of 50%) and that the intervention will increase this rate to 65% (or event rate of 35%, leading to a hazard ratio of 1.5), a total of 225 subjects will be needed.

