## **4. GENERAL ANALYSIS DEFINITIONS**

The general conventions to be used for the statistical analyses and presentation of the data are presented below. Departures from these general conventions may be given in the specific detailed sections of this analysis plan.

1. SAS Version 9 or R Version 3 will be the statistical software package used for all data analyses.
2. Continuous variables will be presented with mean, standard deviation, median (25th percentile, 75th percentile), minimum and maximum values. Categorical variables will be presented as number of subjects and percentage of number of subjects by levels of the variable.
3. The number and percentage of responses will be presented in the form XX (XX) where the percentage is in the parentheses. Unless otherwise specified, the denominator for percentages will be the number of subjects in a given intervention group within the analysis population of interest. The denominator will be included when it differs from the standard analysis population.
4. All summary tables will include the analysis population sample size (i.e., number of subjects).

5. Change from baseline (as applicable) will be calculated for each period as follows:  
Change from baseline = Post-baseline value – baseline value.
6. Date variables will be formatted as DD-MON-YYYY for presentation. In the case of missing day, month, and/or year information, “NA” will be presented. For example, a date with a missing month and day will be presented as NANAYYYY.
7. Unless otherwise stated, statistical comparisons will be performed using two-sided significance tests. An alpha level of 0.05 will determine significance unless otherwise noted for a specified analysis.
8. When count data are presented, the percentage will be suppressed when the count is zero in order to draw attention to the non-zero counts.
9. Unless specified otherwise, data will be presented by intervention and control subjects.

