### **8.1. Analysis Specifications**

#### **8.1.1. Level of Significance**

Unless otherwise specified, all statistical tests will be interpreted at a 2-sided significance level of 0.05, and all confidence intervals at a 2-sided level of 95%.

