#### **8.2.2. Analysis methods**

The primary endpoint is the time to colorectal cancer screening. The date of the pre-intervention survey will be considered Day 0. The date of screening will be considered the date of the event. The date of follow-up phone call will be considered the date of event for subjects for whom a screening result is not recorded in the medical record and who self-report that screening was done. We will conduct a Cox proportional hazards regression model with study arm to evaluate our primary endpoint. In the per-protocol population, we will conduct similar analyses and include age group and gender as independent variables.

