#### 3) Change in screening intent at post-intervention as measured through stages in the Transtheoretical Model.

Screening intent will be measured through stages in the Transtheoretical Model.

Screening intent will be coded as a multi-level categorical variable: “pre-contemplation”, “contemplation” and “preparation” using two specific survey questions (see Table 1). Change in intention to screen for colorectal cancer will compare responses at pre- and post-intervention.

Table 1. Definition for screening intent endpoint

Endpoint	Coding

Change in intent to screen comparing 6months and 12 months to baseline
 
“How much do you agree or disagree: I am intending to have one of the following screening tests within the next 6 months?”
 
(Strongly Disagree, Somewhat Disagree, Somewhat Agree, Strongly Agree)
 
“Have you scheduled one of the above screening tests to be done within the next year?” (No, Yes)
	
As noted above:
 
Precontemplation (Strongly Disagree, Somewhat Disagree) = 0 (reference category)
 
Contemplation (Somewhat Agree, Strongly Agree) = 1
 
Preparation (scheduled a screening test) = 2
 
Did not answer = missing

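### The ITT screening models contain study arm only and leave out baseline intent stage, which is already collected: a missed gain in power, not a bias

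*Combined protocol and SAP*

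**What the plan says.** All references are to the combined protocol and SAP.

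- **Who is enrolled (Section 3).** The population is "Men and women between 50-75 years of age who have never undergone a screening test for colorectal cancer", with a short list of excluded conditions. A subject who has already booked a test is not excluded.
- **When stage is measured (Section 3).** Consenting subjects are randomized at once. Section 3 continues: "Both groups will then undergo a pre-intervention survey designed to assess attitudes towards colorectal cancer screening". The general information, and in the CRCRAT arm the risk score, follow in the same call. Stage is therefore recorded after allocation and before the intervention. Section 8.2.2 makes the survey date Day 0.
- **What stage records (Section 8.3.1, Table 1).** Two questions, on intending a test within 6 months and on having one scheduled within a year, give codes 0, 1 and 2. The top code is "Preparation (scheduled a screening test) = 2". Non-response is set to missing.
- **How screening is analysed (Sections 8.2.2 and 8.3.2).** In the ITT set, "We will conduct a Cox proportional hazards regression model with study arm to evaluate our primary endpoint"; the 6- and 12-month logistic models also have arm as their only independent variable. Age group and gender, the randomization strata in Section 3.3, enter only the per-protocol models. Baseline stage enters no primary or secondary model of screening. It is used in the intent-change model and, as an outcome, in the baseline analysis of Section 9.

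**The concern.** Baseline stage asks whether the outcome event is already intended or arranged, over windows that match the 6- and 12-month endpoints. It is likely to be among the strongest predictors of screening in the dataset. In a Cox or logistic model, omitting a strong predictor moves the arm estimate towards the null relative to the within-stage effect and lowers power. At stake is avoidable loss of power in a trial of 225, when the variable costs nothing more to collect. The choice also has to be made before outcomes are seen, because a covariate added afterwards would look data-driven.

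**Working it through.** **Inputs from the plan.** Two-sided alpha 0.05 (Sections 4 and 8.1.1: "all statistical tests will be interpreted at a 2-sided significance level of 0.05"). Control: "current standard has a screening rate of 50% by 6 months"; intervention 65%; hazard ratio 1.5; 6 months of uniform accrual; at least 12 months of follow-up; "a total of 225 subjects will be needed" (all Section 3.2). Allocation is 1:1 (Section 3.3). Power is not stated; 80% is assumed here.

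**Step 1: reproduce 225.** With exponential times, HR = ln(0.35)/ln(0.50) = 1.0498/0.6931 = 1.515.

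- Schoenfeld events = 4(1.960 + 0.842)²/(ln HR)². HR 1.515 gives 183; HR 1.5 gives 191.
- Freedman events = (1.960 + 0.842)² × [(HR + 1)/(HR − 1)]². HR 1.5 gives 7.849 × 25 = 196.2, so 197.
- Event probability by 12 months: control 1 − 0.50² = 0.750; intervention 1 − 0.35² = 0.8775; mean 0.814. With 12 to 18 months of follow-up the mean is 0.872.
- N = 183/0.814 = 225, 191/0.872 = 220, or 197/0.872 = 226.

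The plan's figure is reproduced at an assumed 80% power. The 50% and 65% are overall rates, so the planned hazard ratio is a marginal one.

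**Step 2: what omitting stage costs.** The stage mix and the hazards by stage are assumptions. Simulation: exponential times, overall control rate fixed at 50% by 6 months, censoring at 12 months. Hazard ratios come from 200,000 subjects and power from 2,000 trials of 225 (simulation error about 1 point: √(0.75 × 0.25/2000) = 0.0097). The within-stage hazard ratio is 1.5 in every stage.

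| Stage mix 0/1/2 (%) | Relative hazards | Intervention rate at 6 months | HR, arm only | HR, adjusted | Power, arm only | Power, adjusted |
|---|---|---|---|---|---|---|
| 40/40/20 | 1/1.5/3 | 63.6% | 1.45 | 1.50 | 69% | 77% |
| 45/50/5 | 1/2/5 | 63.5% | 1.44 | 1.49 | 68% | 77% |
| 40/40/20 | 1/2/5 | 62.5% | 1.41 | 1.51 | 60% | 74% |
| 30/50/20 | 1/3/10 | 61.3% | 1.36 | 1.50 | 51% | 73% |
| Stage not prognostic | 1/1/1 | 64.6% | 1.50 | 1.50 | 77% | 77% |

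The gain is the difference within a row: about 8, 8, 15, 22 and 0 points. The low arm-only powers should not be compared with 80%. In the four prognostic rows the overall difference is only 11.3 to 13.6 points, against the planned 15, so part of that shortfall is a smaller assumed overall effect.

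**Step 3: hold the overall rates at the plan's 50% and 65%.** This needs a within-stage hazard ratio of 1.63 or 1.71, depending on the assumed mix. Arm-only Cox then gives 1.51, with about 78% power. Adjusted Cox gives 1.64 to 1.73, with 90-94% power. The planned effect is kept without adjustment; adjustment adds power.

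**Step 4: no true effect.** Arm-only Cox gives HR 1.00 and rejects in 4.9% of trials; the adjusted model rejects in 5.6%. Both are close to 5%, given a simulation error of about 0.5 points (√(0.05 × 0.95/2000) = 0.0049).

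**Step 5: booked subjects do not respond at all, the others have HR 1.5.**

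| Booked | HR, arm only / adjusted | Power, arm only / adjusted |
|---|---|---|
| 20% | 1.35 / 1.35 | 51% / 51% |
| 10% | 1.40 / 1.42 | 61% / 65% |
| 5% | 1.44 / 1.47 | 68% / 72% |

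A covariate does not restore 1.5. This dilution is a separate mechanism from the one in Step 2.

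The logistic models were not simulated; the figures above apply to the Cox model only.

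**The case against.** **The unadjusted analysis is valid.** Section 3.2 plans from overall rates, and arm-only Cox on all randomized subjects addresses that contrast with correct type I error. A reader might infer that the plan's estimate is biased, or attenuated against its own target. The documents do not support that: Step 3 returns 1.51 when the planned rates hold. The attenuation is relative to a within-stage hazard ratio that the plan never names. This part of the objection stands in full.

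**The size is unknown.** A reader might infer that the trial's real power is near 51%. That figure needs a strongly prognostic assumed mix and a smaller overall effect than planned. The documents give no share of booked subjects and no rate by stage. This stands too; only the range can be shown.

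**Booked subjects belong in the population.** It is tempting to say that they cannot inform the question, but a booked test may not be attended. Section 1 looks to adoption in primary care clinics, where such patients are seen. Their inclusion is a choice of estimand, and Step 5 shows that adjustment would not undo any dilution.

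**Stage is self-reported after open-label allocation.** This is the main drawback of adjusting. If knowing the allocation changed the answers, conditioning on stage could bias the comparison. The survey does precede the intervention content in the same call, so the risk can be stated and checked. It calls for a caveat and an unadjusted estimate alongside, and does not defeat the proposal.

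**Age group and gender also matter.** Section 1 lists both among factors associated with low screening rates, and they are the randomization strata. They should go into the ITT models with stage and should not be displaced by it.

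**Conclusion.** The point holds as a missed gain in efficiency. The ITT Cox and logistic models omit a baseline variable that is already collected and bears directly on the outcome. In the assumed scenarios with a common within-stage hazard ratio of 1.5 and 225 subjects, adjustment raises Cox-model power from about 51-69% to 73-77%. With the overall rates as planned, it raises power from about 78% to 90-94%. If stage is not prognostic, nothing changes. The direction rests on stage predicting screening, which is plausible from the survey questions but not shown in the documents. The size rests wholly on the assumed mixes and hazards. The unadjusted analysis remains a valid test of the marginal effect.

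**What to change.** In Sections 8.2.2 and 8.3.2:

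1. Prespecify pre-intervention intent stage (Table 1 codes 0/1/2, plus a 'not answered' category so that no randomized subject is dropped) as a covariate or analysis stratum in the ITT Cox model, and as a covariate in the ITT logistic models. Include age group and gender as well.
2. State that the adjusted hazard ratio and odds ratios are conditional on these factors, say which estimate is primary, and report the unadjusted one beside it.
3. State the assumption that survey answers are unaffected by allocation, and tabulate baseline stage by arm.
4. As a supportive analysis only, report the effect in subjects with no test scheduled at baseline, because adjustment does not remove dilution from booked subjects. The assumption in item 3 applies here too.

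The cost is SAP wording, fixed before outcomes are examined; no new data are needed. The downsides to state are that the adjusted estimate is conditional on stage, and that it depends on a self-report taken after unblinded allocation.

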## 8.3. Secondary endpoints

### 8.3.1. Definitions

#### 1) Colorectal cancer screening rates at 12 months

The secondary endpoint is whether a subject has had colorectal cancer screening at 12 months. Each subject will have an indicator of “Yes” or “No” for whether they were screened for colorectal cancer at 12 months. This will be determined by a review of subjects’ electronic medical records at 12 months post-randomization. Patient self-report on screening will be used for subjects for whom a screening result is not recorded in the EMR.

#### 2) Colorectal cancer screening rates at 6 months

The secondary endpoint is whether a subject has had colorectal cancer screening at 6 months. Each subject will have an indicator of “Yes” or “No” for whether they were screened for colorectal cancer at 6 months. This will be determined by a review of subjects’ electronic medical records at 6 months post-randomization. Patient self-report on screening will be used for subjects for whom a screening result is not recorded in the EMR.

#### 3) Change in screening intent at post-intervention as measured through stages in the Transtheoretical Model.

Screening intent will be measured through stages in the Transtheoretical Model.

Screening intent will be coded as a multi-level categorical variable: “pre-contemplation”, “contemplation” and “preparation” using two specific survey questions (see Table 1). Change in intention to screen for colorectal cancer will compare responses at pre- and post-intervention.

Table 1. Definition for screening intent endpoint

Endpoint	Coding

Change in intent to screen comparing 6months and 12 months to baseline
 
“How much do you agree or disagree: I am intending to have one of the following screening tests within the next 6 months?”
 
(Strongly Disagree, Somewhat Disagree, Somewhat Agree, Strongly Agree)
 
“Have you scheduled one of the above screening tests to be done within the next year?” (No, Yes)
	
As noted above:
 
Precontemplation (Strongly Disagree, Somewhat Disagree) = 0 (reference category)
 
Contemplation (Somewhat Agree, Strongly Agree) = 1
 
Preparation (scheduled a screening test) = 2
 
Did not answer = missing

### 8.3.2. Analysis methods

To evaluate the secondary endpoint of colorectal cancer screening rates at 12 months and 6 months, we will conduct a logistic regression model in the ITT population,

separately for each time point, with study arm as the independent variable. In addition, we will include age group and gender as independent variables when conducting analyses in the per-protocol population

We will also calculate the proportion of subjects who were screened by study arm at 12 months and 6 months, respectively. For the CRCRAT arm, the numerator will be the total number of subjects who were screened and the denominator will be the total number of subjects randomized to the CRCRAT arm. For the control arm, the numerator will be the total number of subjects who were screened and the denominator will be the total number of subjects randomized to the control arm.

To evaluate the secondary endpoint of change in screening intent at post-intervention, we will use generalized linear mixed models, specifically multinomial logit random effects models, which include study arm and account for time (pre-intervention/post-intervention) and with a random effect for subject.

In the per-protocol population, we will conduct similar analyses and include age group and gender as independent variables.

In addition, we will explore how knowledge, fear, or perception of absolute or relative colorectal cancer risk affect screening intent. We will run separate models to evaluate the impact of these variables by adding each of them to the primary model explained above to determine if there is a change in the outcome. The definitions for each of these variables are based on responses to survey questions and details are provided in Table 2.

Table 2. Definitions for knowledge, fear and perception of colorectal cancer risk

Variable	Coding
Knowledge: Answered "Yes" to "Have you heard of at least one of the following colorectal cancer screening test?" (FOBT, FIT, Stool DNA test, Sigmoidoscopy, Colonoscopy, Double Contrast Barium Enema, CT Colonography, Did not provide answer/not answered)	If nothing is selected, then knowledge = 0 If heard of 1 test, then knowledge = 1 If heard of 2 tests, then knowledge = 2 If heard of 3 or more tests, then knowledge = 3 Did not answer=missing
Fear: "How much do you agree or disagree: I am afraid of finding colon cancer if I got checked" (Strongly Disagree, Somewhat Disagree, Somewhat Agree, Strongly Agree)	Strongly disagree or somewhat disagree = 0 (reference category) Somewhat agree or strongly agree = 1 Did not answer = missing
Perception of absolute colorectal cancer risk:	Very unlikely or unlikely = 0 (reference category)

"How likely are you to get colorectal cancer?"  (Very Unlikely, Unlikely, Neither likely nor unlikely, Likely, Very Likely)
	
Neither likely nor unlikely = 1          Likely or very likely = 2          Did not answer = missing

Perception of relative colorectal cancer risk:  "Compared to the average person, how likely are you to get colon cancer?"  (Very Unlikely, Unlikely, Neither likely nor unlikely, Likely, Very Likely)
	
Very unlikely or unlikely= 0 (reference category)          Neither likely nor unlikely = 1          Likely or very likely = 2          Did not answer = missing

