### **3.3 Randomization and blinding**

Subjects will be randomized 1:1 using block randomization stratified by gender (male/female) and age group (under 60 years old or 60 years old and over) to either the CRCRAT arm or control arm. The randomization scheme will be generated using the 'blockrand' package in R. The 'blockrand' function randomizes subjects to specified groups within sequential blocks; block sizes were randomly chosen from the set of 2, 4, 6, 8. The randomization scheme will be incorporated into REDCap in order to assign participants into the treatment groups. This is an open-label study with no blinding.

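### Change in screening intent: with two answers from one call, the subject-random-effect logit gives an effect size that depends on pre/post agreement and on an unstated fitting method; a baseline-adjusted model is a cheap improvement

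*Combined protocol and SAP*

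**What the plan says.** Section 8.3.2 specifies, for this secondary endpoint, a mixed-model analysis: "specifically multinomial logit random effects models, which include study arm and account for time (pre-intervention/post-intervention) and with a random effect for subject". It lists arm and time but no arm-by-time term. It does not say how the likelihood is to be integrated, which test is used, or whether the target is a subject-specific or a population-level effect. Section 4 allows SAS or R and names no procedure. Section 8.1.1 sets the general rule: "all statistical tests will be interpreted at a 2-sided significance level of 0.05".

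Section 3 puts the pre-intervention survey, the intervention and the second survey in one telephone encounter: "Immediately following these interventions, both arms will undergo a post-intervention survey, which again assesses attitudes towards colorectal cancer screening". Section 8.3.1 defines the endpoint on those two surveys: "Change in intention to screen for colorectal cancer will compare responses at pre- and post-intervention". Table 1 codes intent in three stages, the highest requiring that a test is already scheduled.

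Two other places describe the endpoint differently. Section 7.1 mentions comparing means with allowance for repeated measures, and the label in Table 1 refers to 6 and 12 months against baseline. The explicit promise of odds ratios, in section 9, concerns the baseline regressions and not this model.

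**The concern.** Two answers given close together, in three coarse stages, will often be identical. The top stage can hardly change during a call, since a test would have to be booked in that time (an inference, not a statement in the plan). A logit model with a normal subject effect can reproduce high agreement only with a large random-effect standard deviation. The arm-by-time coefficient is then an odds ratio for one subject with a fixed underlying tendency, which can lie far from the odds ratio that compares the arms. With large variances the common approximations to the likelihood also disagree.

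At stake is the interpretation of a named secondary endpoint. Two competent analysts could both follow section 8.3.2 and report clearly different effect sizes from the same data. The primary time-to-screening analysis is not affected.

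**Working it through.** **1. The plan's own figure.** The only sample size is for the primary endpoint: "a total of 225 subjects will be needed", where "the current standard has a screening rate of 50% by 6 months" and the intervention rate is 65% (hazard ratio 1.5). Power is not stated; take 80%, two-sided 0.05.
- Schoenfeld events: 4 × (1.960 + 0.842)² / (ln 1.5)² = 191. Freedman events: (2.5/0.5)² × (1.960 + 0.842)² = 197 after rounding up.
- Mean event probability with exponential times, 6 months' accrual and 12-18 months' follow-up: (0.820 + 0.922)/2 = 0.871.
- N = 191/0.871, about 220, or 197/0.871, about 227. The plan's 225 is reproduced within 3%.

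No power, effect or agreement is given for the intent endpoint, so everything below rests on assumptions.

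**2. Assumed inputs.** Intent is reduced to two levels (above precontemplation or not), with 113 and 112 subjects (225 randomised 1:1). Before the call 50% are above precontemplation; afterwards 52% in control and 62% in CRCRAT. Population odds ratio: (0.62/0.38)/(0.52/0.48) = 1.51. An arm-by-time term is added throughout steps 3 and 4.

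**3. Size of the coefficient.** In a random-intercept logit, a subject's odds of moving up rather than down equal exp(time effect in that arm), whatever the intercept. The ratio of these discordant odds between arms is therefore the subject-specific odds ratio. At 90% control agreement: (0.135/0.015)/(0.06/0.04) = 9.0/1.5 = 6.0. Fits to expected counts:

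| Control agreement | Up/down, control | Up/down, CRCRAT | Discordant ratio | Random-effect SD | OR, accurate integration (÷ 1.51) | OR, Laplace | OR, PQL |
|---|---|---|---|---|---|---|---|
| 70% | 0.16/0.14 | 0.22/0.10 | 1.93 | 2.0 | 1.95 (1.3) | 1.84 | 1.56 |
| 80% | 0.11/0.09 | 0.17/0.05 | 2.78 | 3.6 | 2.78 (1.8) | 2.42 | 1.63 |
| 90% | 0.06/0.04 | 0.135/0.015 | 6.0 | 7.4 | 6.8 (4.5) | 3.3 | 1.73 |
| 95% | 0.035/0.015 | 0.125/0.005 | 10.7 | 13 | about 26 (17), unstable | 4.1 | 1.78 |

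Adaptive quadrature with 3 to 15 points gave 4.9-6.3 at 90% and 11-87 at 95%. A 30% baseline gave 1.89, 2.67, 6.3 and 22 by accurate integration, against a population value of 1.54. A further refit gave SD 3.7 and median OR 2.6 at 80%, and SD 7.2 and median OR 6.3 (10th-90th percentile 2.4 to 33) at 90%.

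**4. Power.** Simulated with 500-600 runs per setting; Monte Carlo error about 2 points.

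| Analysis | 70% | 80% | 90% | 95% |
|---|---|---|---|---|
| Mixed model, arm-by-time, likelihood ratio | 28 | 40 | 60 | 70 |
| Mixed model, arm-by-time, Wald | 28 | 38 | 51 | 22 |
| Marginal (GEE-type) model, arm-by-time | 29 | 41 | 60 | 76 |
| Mixed model with common baseline, likelihood ratio | 39 | 49 | 65 | 77 |
| Logistic model of post on arm and pre | 39 | 49 | 66 | 81 |
| Mixed model, arm term without arm-by-time, likelihood ratio | 16 | 15 | 15 | 21 |

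The baseline-adjusted model leads the mixed model by 39 − 28 = 11, 49 − 40 = 9, 66 − 60 = 6 and 81 − 70 = 11 points. The further refit gave 47 − 35 = 12 and 65 − 57 = 8, with 12-14% for the arm term as written. With a 30% baseline the gaps at 90% and 95% were 4 and 13. About 5 to 12 points is a fair summary.

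The arm term as written is weak because it averages over both surveys. The arms do not differ before the call and differ by ln 1.51 = 0.41 after it, so on the population scale it captures about 0.41/2 = 0.20.

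**5. Three stages.** A three-stage version of the baseline-adjusted model held its error rate (about 4%) and gave unbiased standardised proportions. The arm coefficient for preparation was near-separated in 35-39% of runs.

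**The case against.** A mixed model is a recognised repeated-measures method, and a subject-specific odds ratio is a different estimand, not a biased one. Nor does the plan say that odds ratios from this model will be reported. All of this stands; the defect is that the plan neither chooses an estimand nor fixes how it is computed.

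The inflation is also conditional. At 70-80% agreement the ratio is 1.3 to 1.8, and under PQL it stays at or below about 1.2 at every level. This stands too, although the gap between PQL and accurate integration is itself the dependence on fitting method.

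A reader might infer three stronger things that are not supported.
- *The random effect costs power in general.* By likelihood ratio the mixed model matches the marginal model up to 90% agreement. A mixed model that keeps the random effect but shares the baseline recovers almost all of the gap up to 90% (39, 49 and 65 against 39, 49 and 66) and most of it at 95% (77 against 81). Only Wald tests at 90-95% lose heavily, and the plan does not specify Wald.
- *The odds ratio is identified mainly by the normal assumption.* In the two-level model the discordant-pair ratio identifies it whatever the distribution. A true value of 3.0 was returned under normal, two-point and uniform random effects.
- *False positives are inflated.* The null runs of the mixed-model arm-by-time test gave 3-5%.

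Finally, the replacement has its own weak spot: sparse movement into preparation can leave that coefficient poorly determined. Standardised proportions held up, so the report should rest on those.

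**Conclusion.** The concern holds in a conditional form. If pre/post agreement is high, the planned random-effect logit yields an odds ratio that departs from the population value of about 1.5: roughly 1.3-fold at 70% agreement, 1.8-fold at 80% and 4-fold or more at 90% with accurate integration. That value also varies with a fitting method the plan leaves open. High agreement is plausible from the design, but the documents do not show it, so it cannot be said that the random effect will be degenerate.

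The power shortfall of about 5 to 12 points against baseline adjustment is a separate matter that comes mainly from baseline handling. The weakest element is the arm term as written, at about 12-21% power, because it does not measure change.

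These figures rest on a two-level reduction of a three-stage outcome, an assumed 50% baseline (30% gave a similar pattern with accurate integration), and assumed shifts of 2 and 12 points. This should be changed before analysis, but it concerns one of three secondary endpoints.

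**What to change.** In section 8.3.2, make the main analysis of change in intent a multinomial logistic model with one record per subject: post-intervention stage as outcome, study arm as the factor and pre-intervention stage as covariate. Test arm with a likelihood-ratio test. Report arm-standardised stage proportions and their between-arm differences with 95% confidence intervals, and do not rely on the preparation-stage coefficient. Keep the mixed model as a sensitivity analysis, with an arm-by-time term, adaptive quadrature and a statement that its odds ratio is subject-specific. Align section 7.1 and the label in Table 1 with this definition.

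The cost is SAP wording and a simpler model, with no change to data collection. The downside is that a subject missing either stage drops out unless imputed under section 8.1.2, so the text should say that imputation will be used.
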